No direct benefits are expected for participants. The current study is designed to address the important issue of learning after aphasia-inducing stroke. Speech-language therapy is the treatment for aphasia and relies heavily on behavioral therapies that engage distinct neural and behavioral systems, but are not currently evaluated. In order to better tailor treatment to individuals and more effectively predict outcomes, we must equip clinicians with ways to characterize learning in individual patients, further identifying stimulus or task manipulations that lead to the development of effective strategies for patients.

EQUITABLE SELECTION OF SUBJECTS

The risks and benefits of the research must be fairly distributed among the populations that stand to benefit from it. No group of persons, for example, men, women, pregnant women, children, and minorities, should be categorically excluded from the research without a good scientific or ethical reason to do so. Please provide the basis for concluding that the study population is representative of the population that stands to potentially benefit from this research.

There are no exclusionary subject criteria with respect to gender, race or ethnicity. Minors will not be studied, as the incidence of stroke in younger individuals is low, and furthermore, the mechanisms of neural plasticity in adults and children are different, resulting in different impacts of stroke in children.

When people who do not speak English are excluded from participation in the research, provide the scientific rationale for doing so. Individuals who do not speak English should not be denied participation in research simply because it is inconvenient to translate the consent form in different languages and to have an interpreter present.

One aspect of this research is to examine learning in the context of language deficits. We are excluding non-English speakers because we are testing speech and language ability in the individuals with aphasia.

For guidance, refer to the following Partners policy: Obtaining and Documenting Informed Consent of Subjects who do not Speak English https://www.partners.org/Assets/Documents/Medical-Research/Clinical- Research/Non-English-Speaking-Subjects.pdf

RECRUITMENT PROCEDURES

Explain in detail the specific methodology that will be used to recruit subjects. Specifically address how, when, where and by whom subjects will be identified and approached about participation. Include any specific recruitment methods used to enhance recruitment of women and minorities.

Individuals with aphasia will be recruited by referral from physicians, speech-language pathologists, neuropsychologists. We will mail and email recruitment letters to neurologists and speech pathologists in the greater Boston area. Interested professionals will describe the study to the potential participants and ask them to contact the researcher if they are interested in participating in the study. Individuals who have participated in lab for previous studies and have indicated that they agree to be contacted for future studies may be contacted. A member of the research team will contact these participants via phone call.

Individuals with aphasia will also be recruited from the MGH-Institute of Health Professions Aphasia Center. Speech language pathologist will share study flyers with individuals with aphasia and ask if individuals are interested in meeting a member of the research team to learn more about the study. If they express interest, a member of the research team will be invited to come to the end of an upcoming scheduled therapy session to talk more about the study. It will be clearly communicated that the treating Speech language pathologist has no affiliation to the research study and that expressing or not expressing an interest to speak to research staff, in no way impacts the therapy services they receive in the MGH-IHP Aphasia Center.

In addition, participants will be recruited via word of mouth, flyers/presentations, and email posts on listservs. We will also recruit via RSVP for health. Information about research studies will be posted on the Institute's website.

Provide details of remuneration, when applicable. Even when subjects may derive medical benefit from participation, it is often the case that extra hospital visits, meals at the hospital, parking fees or other inconveniences will result in additional out-of-pocket expenses related to study participation. Investigators may wish to consider providing reimbursement for such expenses when funding is available

Participants will be compensated for their time and participation in the study. They will be compensated \$10/hour of participation in behavioral sessions (anticipate ~ \$70/participant to complete all behavioral tasks and assessments). Participants will be compensated more than \$50 and therefore will be compensated via check. We will notify participants that a social security number and valid US address will be collected and reported in the MGB eCheck submission.

Participants who complete a structural scan will be compensated an additional \$50.

Participants driving to the research site may park in the Building 199 parking garage in the Charlestown Navy Yard. Participants will be given a parking voucher on each day of study participation that they can use in Parking garage buildings upon exit without incurring any personal costs.

For guidance, refer to the following Partners policies: Recruitment of Research Subjects https://www.partners.org/Assets/Documents/Medical-Research/Clinical-Research/Recruitment-Of-Research-Subjects.pdf

Guidelines for Advertisements for Recruiting Subjects https://www.partners.org/Assets/Documents/Medical-Research/Clinical-Research/Guidelines-for-Advertisements.pdf

Remuneration for Research Subjects

https://www.partners.org/Assets/Documents/Medical-Research/Clinical-Research/Remuneration-for-Research-Subjects.pdf

CONSENT PROCEDURES

Explain in detail how, when, where, and by whom consent is obtained, and the timing of consent (i.e., how long subjects will be given to consider participation). For most studies involving more than minimal risk and all studies involving investigational drugs/devices, a licensed physician investigator must obtain informed consent. When subjects are to be enrolled from among the investigators' own patients, describe how the potential for coercion will be avoided.

Once interest in participating in the study is expressed, one of the research staff involved in this study will establish contact with potential participants over the phone or via email. The research project will be explained and screening questions will be asked. and Interested persons will be invited to the research site to discuss the study.

The patient and his/her spouse/next of kin will be invited to the laboratory to discuss the study with a member of the research staff with speech-language pathology training and experience working with individuals with aphasia. In this meeting, research staff will explain the study using simple language. She/he/they will also have sample materials from the study, such as pictures of stimuli to help explain study paradigms. Extra care will be taken to ensure that subjects understand the nature of the study. We will offer to read the consent form to these individuals as reading can be difficult, and information will be reiterated verbally. Individuals and family members will be encouraged to interrupt, ask questions and seek clarifications. They will be given time to assess presented information and formulate questions. Individuals with aphasia are considered capable of making informed decisions and provide consent as indicated in the National Aphasia Association Bill of Rights (2005). Therefore, family members may be present when study procedures are explained, but individuals with aphasia will be giving or declining to give informed consent. The purpose, procedures, possible benefits and risks of the study will be explained. Potential participants will also be instructed that they can withdraw from the study at any time.

NOTE: When subjects are unable to give consent due to age (minors) or impaired decisionmaking capacity, complete the forms for Research Involving Children as Subjects of Research and/or Research Involving Individuals with Impaired Decision-making Capacity, available on the New Submissions page on the PHRC website:

https://partnershealthcare.sharepoint.com/sites/phrmApply/aieipa/irb

For guidance, refer to the following Partners policy: Informed Consent of Research Subjects: https://www.partners.org/Assets/Documents/Medical-Research/Clinical-Research/Clinical-Research/Informed-Consent-of-Research-Subjects.pdf

DATA AND SAFETY MONITORING

Describe the plan for monitoring the data to ensure the safety of subjects. The plan should include a brief description of (1) the safety and/or efficacy data that will be reviewed; (2) the planned frequency of review; and (3) who will be responsible for this review and for determining whether the research should be altered or stopped. Include a brief description of any stopping rules for the study, when appropriate. Depending upon the risk, size and complexity of the study, the investigator, an expert group, an independent Data and Safety Monitoring Board (DSMB) or others might be assigned primary responsibility for this monitoring activity.

NOTE: Regardless of data and safety monitoring plans by the sponsor or others, the principal investigator is ultimately responsible for protecting the rights, safety, and welfare of subjects under his/her care.

Forms containing personally identifying information such as contact information and questions related to eligibility, are programmed in RedCap with responses directly entered into RedCap. Cognitive-linguistic assessment data is collected on paper forms that will be kept in a locked filing cabinet at the MGH-IHP to which only the PI and approved study staff have access. Information will be transferred into a secure HIPAA compliant web-based application: RedCap to which only approved researchers have access.

Digital data (such as study reaction time, accuracy files, certain cognitive-linguistic assessments such as the TALSA and eye tracking data) will initially be collected on an encrypted, password protected laptop (accessed by the PI and study staff) or desktop computer. Data will be transferred to Dropbox, a secure network or web-based electronic lab notebook, LabArchives, maintained by MGB, which can only be accessed by the PI and approved study staff via electronic ID. These digital files will be coded with identification codes and will not contain personally identifiable information. Deidentified standardized assessment scores will be transferred from paper forms to digital forms in RedCap. Video data will be recorded and kept on MGB Dropbox and accessed only by approved researchers. Deidentified video clips will be kept for education purposes.

MRI imaging data obtained at the Martinos Center are stored and analyzed on an MGB-hosted secure cluster to which only approved research staff have access.

De-identified data are kept for possible future analyses, which will be submitted for approval. If we re-analyze data in the future, we will notify and submit an application for approval from the IRB.

Describe the plan to be followed by the Principal Investigator/study staff for review of adverse events experienced by subjects under his/her care, and when applicable, for review of sponsor safety reports and DSMB reports. Describe the plan for reporting adverse events to the sponsor and the Partners' IRB and, when applicable, for submitting sponsor safety reports and DSMB reports to the Partners' IRBs. When the investigator is also the sponsor of the IND/IDE, include the plan for reporting of adverse events to the FDA and, when applicable, to investigators at other sites.

NOTE: In addition to the adverse event reporting requirements of the sponsor, the principal investigator must follow the Partners Human Research Committee guidelines for Adverse Event Reporting

Since the risks associated with participation in this study are low, we do not anticipate serious adverse events. In the event of internal, external adverse events, of unanticipated adverse device effects, deviations, or breaches of confidentiality; the event will immediately be assessed and the IRB office will be contacted. A detailed description of the event will be provided to the IRB. Furthermore, if it is ever deemed that the risks associated with participation places subjects at increased harm, the IRB will be notified.

MONITORING AND QUALITY ASSURANCE

Describe the plan to be followed by the principal investigator/study staff to monitor and assure the validity and integrity of the data and adherence to the IRB-approved protocol. Specify who will be responsible for monitoring, and the planned frequency of monitoring. For example, specify who will review the accuracy and completeness of case report form entries, source documents, and informed consent.

NOTE: Regardless of monitoring plans by the sponsor or others, the principal investigator is ultimately responsible for ensuring that the study is conducted at his/her investigative site in accordance with the IRB-approved protocol, and applicable regulations and requirements of the IRB.

The PI or study staff will conduct ongoing review of data to ensure completeness, accuracy and compliance with protocols. Quarterly review will ensure that participant inclusion is in adherence with enrollment criteria, that records of subject enrollment are up to date, and that procedures and study visits are being completed as proposed. Review will be completed by the PI or study staff. In the event of an adverse event, the event will be immediately reviewed. Continuing reviews will be submitted in accordance with the IRB.

For guidance, refer to the following Partners policies: Data and Safety Monitoring Plans and Quality Assurance https://www.partners.org/Assets/Documents/Medical-Research/Clinical-Research/DSMP-in-Human-Subjects-Research.pdf

Reporting Unanticipated Problems (including Adverse Events) https://www.partners.org/Assets/Documents/Medical-Research/Clinical-Research/Clinical-Research/Reporting-Unanticipated-Problems-including-Adverse-Events.pdf

PRIVACY AND CONFIDENTIALITY

Describe methods used to protect the privacy of subjects and maintain confidentiality of data collected. This typically includes such practices as substituting codes for names and/or medical record numbers; removing face sheets or other identifiers from completed surveys/questionnaires; proper disposal of printed computer data; limited access to study data; use of password-protected computer databases; training for research staff on the importance of confidentiality of data, and storing research records in a secure location.

NOTE: Additional measures, such as obtaining a Certificate of Confidentiality, should be considered and are strongly encouraged when the research involves the collection of sensitive data, such as sexual, criminal or illegal behaviors.

All materials (history forms, data obtained during behavioral tasks) are for research purposes only and will be kept in confidence. History forms containing personally identifying information are maintained in RedCap, a secure database to which only study staff have access. Cognitive-linguistic assessments) collected on paper will be kept in a locked filing cabinet at the MGH-IHP to which only the PI and approved study staff have access.

During analysis, de-identified data will be pulled from RedCap coded with identification codes and will not contain personally identifiable information. The RedCap database to which only study staff have access will be the only location that stores the link between study codes and subject identifying information.

Once participants have been paid for their participation, any records containing social security numbers will be destroyed and permanently removed from their research record.

SENDING SPECIMENS/DATA TO RESEARCH COLLABORATORS OUTSIDE PARTNERS

Specimens or data collected by Partners investigators will be sent to research collaborators outside Partners, indicate to whom specimens/data will be sent, what information will be sent, and whether the specimens/data will contain identifiers that could be used by the outside collaborators to link the specimens/data to individual subjects.

N/A. Data will not be sent to research collaborators outside of Partners.

Specifically address whether specimens/data will be stored at collaborating sites outside Partners for future use not described in the protocol. Include whether subjects can withdraw their specimens/data, and how they would do so. When appropriate, submit documentation of IRB approval from the recipient institution.

N/A. No data will be stored outside of MassGeneralBrigham.

RECEIVING SPECIMENS/DATA FROM RESEARCH COLLABORATORS OUTSIDE PARTNERS

When specimens or data collected by research collaborators outside Partners will be sent to Partners investigators, indicate from where the specimens/data will be obtained and whether the specimens/data will contain identifiers that could be used by Partners investigators to link the specimens/data to individual subjects. When appropriate, submit documentation of IRB approval and a copy of the IRB-approved consent form from the institution where the specimens/data were collected.

N/A. No data will be received from outside of MassGeneralBrigham.

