Cover page for clinicaltrials.gov

Study Title	Determining the Implicit and Rule-based Learning Ability of Individuals With Aphasia to Better Align Learning Ability and Intervention
NCT Number	05119023
Document Description	IRB approved protocol
Document Date	Document version date = 8/30/22

PARTNERS HUMAN RESEARCH COMMITTEE PROTOCOL SUMMARY

Answer all questions accurately and completely in order to provide the PHRC with the relevant information to assess the risk-benefit ratio for the study. Do not leave sections blank.

PRINCIPAL/OVERALL INVESTIGATOR

[name]

PROTOCOL TITLE

Determining the implicit and rule-based learning ability of individuals with aphasia to better align learning ability and intervention

FUNDING

NIH NIDCD R21 DC019203-01

VERSION DATE

Version 7: 8/30/22

SPECIFIC AIMS

Concisely state the objectives of the study and the hypothesis being tested.

The objective of this study is to examine learning in individuals with post-stroke aphasia (acquired language impairment). We aim to determine a behavioral phenotype of learning for people with aphasia (PWA), examining how cognitive-linguistic variables and stroke characteristics (lesion size and location) relate to learning.

To this end, the aims are as follows:

Aim 1. Determine the presence of selective deficits in observational (implicit) and rulebased learning in individuals with aphasia. Participants in our study will be stratified in to one of four learning profiles: learning under (a) both conditions, (b) rule-based conditions only, (c) observational conditions only, and (d) no condition. Pilot work conducted in eighteen individuals with aphasia has identified equal percentages of learners of type a, c and d (20% of pilot participants in each stratification) with 40% showing learning under rule-based conditions only, supporting the hypothesis that differences in learning profile arise among PWA.

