Test of Every Day Attention (TEA; Robertson et al., 2001)	Evaluates auditory sustained attention, visual and verbal working memory
Temple Assessment of Language and (Verbal) Short-term Memory in Aphasia (TALSA; Martin et al., 2018) listening span, synonymy triplet and lexical comprehension subtests	Evaluates lexical-semantic short-term memory and working memory
Berg Card Sorting Test (http://pebl.sourceforge.net/)	Evaluates executive function (self monitoring, flexibility, attention, shifting)
Northwestern Assessment of Verbs and Sentences (NAVS; Thompson, 2012) sentence production priming and sentence comprehension subtests	Evaluates grammatical abilities/syntax. Higher scores on canonical > noncanonical sentences indicate the presence of agrammatism
Villard Sustained Attention Task (Villard & Kiran, 2015)	Evaluates visual sustained attention

Tompkins Listening span task	Evaluates auditory-verbal working memory
(Tompkins et al., 1994)	

Brief overview of statistical methods

Aim 1. Determine the presence of selective deficits in observational (implicit) and rule-based learning in individuals with aphasia.

Observational learning tasks: Participants will complete two observational learning tasks: Serial Response Time (SRT) Observational learning and Artificial Grammar Learning (AGL) Observational learning.

For the SRT observational learning task (described below), responses are made via eye gaze into a visual area of interest (AOI). Reaction times (RTs) are recorded as the time between target onset and gaze fixation within the target AOI. A trial is considered incorrect if an eye fixation was made that does not correspond to the target AOI. RTs for correct trials are examined. Outlier RTs three standard deviations above the mean RT of each block will be removed. A score of learning will be computed by comparing RTs on the last (7th) sequenced block of trials with RTs on the following (8th) pseudorandomized block (Schwarb & Schumacher, 2012). A Cohen's *d* effect size (ES) of observational learning will be calculated for each individual participant that compares mean RTs on the final sequenced block (S7) and the pseudorandom block (PS8) using pooled standard deviations. Any participant producing a small ES of 0.2 or above (Cohen, 1988) will be classified as a learner in the observational learning condition.

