For the AGL Observational learning task (described below), data are collected on the accuracy of match, non-match responses during training computed as a percent correct. Data are also collected as a percent correct score in the testing phase. Each stimulus will be presented two times in testing and accuracy will be coded as 1 (correct) if on both presentations the participant made a correct response. If the item is classified incorrectly on 1 presentation or both presentations, the response for that item will be coded as 0 (incorrect). A threshold probability of 25% will be utilized to characterize performance as above chance and classify a participant as a learner under AGL Observational conditions.

Rule based learning task: For the rule-based task (described below), data are collected on the number of rules learned within the instruction period. Data are also collected on accuracy in testing. An accuracy score is computed for the test phase and is the dependent measure of rule learning. We will compute binomial chance probability. A threshold probability of 50% will be utilized to characterize performance as above chance and classify a participant as a learner under rule-based methods. Any participant whose score does not meet criterion, will be stratified as demonstrating selective weakness in rule-based learning.

Aim 2. Determine the predictors of observational and rule-based learning, incorporating subjectspecific measures of structural brain damage, aphasia severity, attention, verbal working memory and executive function.

Calculations of lesion volume and spared tissue. Implicit and rule-based learning are thought to engage partially overlapping brain networks that include the striatum, dorsolateral prefrontal cortex, medial prefrontal cortex, anterior cingulate, thalamus, medial temporal lobe, superior and inferior parietal cortex, occipital gyrus and cerebellum (e.g.,Destrebecqz et al., 2005; Paniukov & Davis, 2018; Peigneux et al., 2000; Reber, 2013; Schneyer et al., 2009; Squire, 1992; Willingham et al., 2002). The amount of spared tissue within regions of this network will be calculated based on previously established methods (Kiran et al., 2015; Meier et al., 2016; Sims et al., 2016). For each PWA a lesion map, in which the lesioned voxels are

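### Aim 1 calls a deficit selective when a person passes one cut-off and fails another, without testing whether the two performances differ within that person

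*Combined protocol and SAP*

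**What the plan says.** The first aim is to "Determine the presence of selective deficits in observational (implicit) and rulebased learning in individuals with aphasia". The Specific Aims state: "Participants in our study will be stratified in to one of four learning profiles". Profile (a) is learning under both conditions, (b) rule-based only, (c) observational only and (d) neither.

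The Brief overview of statistical methods sets one cut-off per task:

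- SRT observational: "Any participant producing a small ES of 0.2 or above" counts as a learner. The effect size compares two blocks of the same task.
- AGL observational: "A threshold probability of 25% will be utilized to characterize performance as above chance".
- Rule-based: "A threshold probability of 50% will be utilized to characterize performance as above chance". The paragraph adds "We will compute binomial chance probability" but gives no alpha or critical score.

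The rule-based paragraph ends by attaching the selective-weakness label to anyone below its criterion, with no reference to observational performance. The plan does not say how the SRT and AGL results combine into one observational pass.

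The Specific Aims report a pilot in eighteen people with 20% in each of (a), (c) and (d), "with 40% showing learning under rule-based conditions only, supporting the hypothesis that differences in learning profile arise among PWA".

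**The concern.** A selective deficit is a statement about a contrast: this person does worse in one mode of learning than in the other. Passing one threshold and failing another does not establish that contrast. Two scores can lie just either side of their cut-offs and be statistically indistinguishable, and the thresholds may differ in strictness. The checks that are planned look at one task at a time, either block against block or accuracy against chance.

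The rule-based label has a separate fault. Someone who fails everything belongs in profile (d), yet the rule-based paragraph would call that person selectively weak.

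What is at stake is the Aim 1 conclusion. An unknown share of profiles (b) and (c) could be classification error, and the plan has no step that would show how large that share is.

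**Working it through.** **1. The pilot figure.** 20% of 18 is 3.6 people, so the shares are rounded. In the order a/b/c/d, counts of 4/7/4/3 give 22/39/22/17%, which match to the nearest 10%. Strictly equal a, c and d would need 4/6/4/4 (22/33/22/22%) or 3/9/3/3 (17/50/17/17%). Taking the stated shares, the rule-based pass rate is a + b = 60%, the observational pass rate is a + c = 40%, and the discordant share is b + c = 60%.

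**2. Discordance when true ability is identical.** Give each person one true ability, measured by both tasks with reliability ρ (assumed .5 to .9). The two scores are then bivariate normal with correlation ρ, and

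discordant share = pA + pB − 2 × P(both pass).

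At 50% pass rates this reduces to arccos(ρ)/π.

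| Assumed reliability | Pass rates 50% / 50% | Pass rates 60% / 40% |
|---|---|---|
| .5 | 33% | 37% |
| .7 | 25% | 30% |
| .9 | 14% | 22% |

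In the last column, unequal strictness alone gives 60% − 40% = 20% even with perfect measurement. If all 75 planned participants had equal ability, the range is 75 × .144 ≈ 11 to 75 × .368 ≈ 28 people.

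**3. Who is affected.** This step assumes 30 to 100 trials per SRT block and 20 to 60 rule-based test items. It takes SRT against the rule-based task and reads the 50% rule either as a raw cut or as a one-sided .05 binomial cut. P(one-sided) = pA(1 − pB) + pB(1 − pA).

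| True performance on both tasks | Raw cut | Binomial cut |
|---|---|---|
| No learning (d = 0, 50% correct) | 43–47% | 10–25% |
| Modest (d = 0.2, 60% correct) | 50% | 50% |
| d = 0.3, 65% correct | 25–39% | 37–58% |
| Clear (d = 0.6, 80% correct) | 0–7% | 0–24% |

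**4. The unstated combination rule.** Suppose each of the three tasks is passed independently with the same probability p. The observational pass rate q is 1 − (1 − p)² if either task suffices and p² if both are needed. P(one-sided) = p(1 − q) + q(1 − p). At p = .6, .8 and .9 this gives 43%, 22% and 11% if either suffices, and 53%, 42% and 25% if both are required.

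**5. Adding a difference test.** In the model of step 2 (1,000,000 simulated people), require a discordant profile and also |zA − zB| / √(2(1 − ρ)) > 1.96. The share called selective falls to 4.0% at reliability .5, about 3.3% at .7 and 2.0% at .9. That is about 2 to 3 of 75 people.

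**The case against.** **The profiles are defined by criterion.** They describe learning under one condition only, and replacing them with relative scores would change the question. Scores standardised to the sample mean remove any weakness that the whole group shares in one mode, and there is no control group to recover it. This stands, and it is why the fix keeps the profiles and restricts only the word selective.

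**The size is not known.** A reader might infer that equally able people will often be mislabelled. The documents do not support that: they give no trial counts, item counts, pass probabilities or reliability, and clear learners are rarely affected on a raw cut.

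**The pilot does not show that the labels are noise.** A reader might note that two unrelated pass/fail results with 60% and 40% pass rates would give .6 × .4 = 24%, .6 × .6 = 36%, .4 × .4 = 16% and .4 × .6 = 24%, close to the stated 20/40/20/20%, and test the split against independence. That test addresses the wrong null. Equal ability predicts that passes go together, whereas truly separate abilities also give independence. The pilot odds ratio is (20 × 20)/(40 × 20) = 0.5, in the opposite direction, and its 60% discordance exceeds the 37% that equal ability predicts at reliability .5. With 10 or 11 of 18 discordant, the one-sided binomial probability at 36.8% is .08 or .03. Very unreliable labels remain possible, since zero reliability predicts 52%. The pilot is also offered only as support for differing profiles. It neither establishes within-person selectivity nor refutes it.

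**The consequence is limited.** The Aim 2 models and the power calculations use continuous scores, and the protocol states that this is not a treatment or diagnostic study. This bounds the point to Aim 1.

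**Conclusion.** The concern holds for the Aim 1 inference. Selectivity is read from two separate cut-offs, no within-person difference is tested, and the rule-based paragraph extends the label to people who fail everything. These points rest on the text alone.

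The size rests on assumptions. If true ability were identical on both tasks and reliability lay between .5 and .9, 33% to 14% would get a one-sided profile at equal 50% pass rates, and 37% to 22% at the pilot pass rates. The problem is concentrated in people at chance or near a cut-off. The rounded pilot shares do not settle the matter, and the Aim 2 regressions are not directly affected.

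**What to change.** 1. Keep the four criterion-based profiles as a descriptive classification.
2. Use the word selective for (b) or (c) only when the profile is discordant and the person's difference between observational and rule-based performance has a 95% interval excluding zero, with trial-level error (for example from a bootstrap over trials). Otherwise report: discordant, no selective difference shown.
3. State the scale of the difference. If scores are standardised to the sample mean, say that this shows relative strength only.
4. Remove the selective-weakness label in the rule-based paragraph for people who also fail observational learning.
5. State how SRT and AGL combine into one observational result, and the critical score for each accuracy cut-off.
6. Report split-half (odd/even trial) reliability of the labels beside the four-cell table.

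All of this uses data already to be collected. The cost is revised analysis wording and a modest amount of computation. The downside is that fewer people receive a selective label, and some individual intervals will be wide, especially if the tests are short.
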